# 7.7.5 Electrocardiograms

The following quantitative ECG measurements will be taken in triplicates during the study:

- heart rate (beats/min);
- RR interval (msec);
- PR interval (msec);
- QRS interval (msec);
- QT interval (msec);
- Fridericia corrected QT (QTcF) interval (msec);

The average QTcF interval (msec) values and changes from baseline will be summarized by treatment group and overall plitidepsin, and by visit using standard descriptive statistics for the As Treated population.

The Baseline value will be defined as last scheduled or unscheduled non-missing value collected prior to the first dose of the first study drug administration. Assessments carried out on day of first study drug administration are considered to have taken place before the study drug administration, if the corresponding times have not been recorded. For post-baseline, only data from scheduled visits will be included in the summary tables.

In addition, the number and percentage of patients with a potentially clinically important ECG result defined as:

- Average QTcF interval value > 500 msec
- Change from baseline in QTcF interval > 30 msec

will be tabulated by treatment group and overall plitidepsin, and visit for the As Treated population.

Patients participating in the QTc substudy will have additional measurements by continuous 12-lead ECG automated monitoring over Days 1 to 3. The QTc substudy will be managed by a vendor (ERT - eResearchTechnology, Inc). The data analysis methods will be detailed in a separate statistical analysis plan and results will be reported separately.

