#### CONFIDENTIAL

\*Body weight and height should be measured at screening.

- 1 Informed consent: Must be obtained before the patient undergoes any study-specific procedure
- 2 Selection criteria: Confirm that patient meets all inclusion criteria and none of the exclusion criteria
- 3 Vital signs: Temperature, sitting blood pressure, heart rate, respiratory rate, PaO2 (obtained either by arterial blood gas analyses or from saturation of oxygen (SpO2) by pulse oximetry, and its respective FiO2 to be measured at screening, on Days 1 to 3 just before start and end of each plitidepsin infusion (plitidepsin groups)/once daily on Days 1 to 3 (control group), further once daily while the patient is hospitalised, and on Days 8, and 31 (±3 days). To estimate the PaO2/FiO2 ratio, the required equation would be used for imputing PaO2 from SpO2, and the information on the oxygen delivery devices and oxygen flow prescribed would be utilised for imputation of FiO2.
- 4 ECG: QTcF prolongation to be assessed at screening and on Days 1, 3 (postinfusion), and 31 (±3 days), and any QTcF values >500 msec will be flagged as increasing the likelihood of the treatment being proarrhythmic (per ICH Guidance E14)
- 5 Haematology: RBC, haemoglobin, haematocrit, WBC with differential, platelet count. Testing to be performed by the local laboratory for screening and by central laboratory for on-study tests (tests performed within 24 hours of screening do not have to be repeated)

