### 3.15 Electrocardiograms (ECGs)

#### Table 14.3.6.1 Summary of 12-Lead Electrocardiogram (ECG) Parameters - Change from Baseline (As Treated Population)

Parameter (unit)								
	Plitidepsin 2.5mg (N=XXX)		Plitideps (N=X	sin 1.5mg XXX)	Plitidepsin Total (N=XXX)		Control Arm (N=XXX)	
Visit		Change from		Change from Change from				Change from
Statistic	Value at Visit	Baseline	Value at Visit	Baseline	Value at Visit	Baseline	Value at Visit	Baseline
Baseline								
n	XXX		XXX		XXX		XXX	
Mean (SD)	xx.xx (xx.xxx)		xx.xx (xx.xxx)		xx.xx (xx.xxx)		xx.xx (xx.xxx)	
Median	XX.XX		XX.XX		XX.XX		XX.XX	
Q1, Q3	xx.xx, xx.xx		xx.xx, xx.xx		xx.xx, xx.xx		xx.xx, xx.xx	
Min, Max	XX.X, XX.X		xx.x, xx.x		xx.x, xx.x		xx.x, xx.x	
< <day x="">></day>								
n	XXX	XXX	XXX	XXX	XXX	XXX	XXX	XXX
Mean (SD)	xx.xx (xx.xxx)	xx.xx (xx.xxx)	xx.xx (xx.xxx)	xx.xx (xx.xxx)	xx.xx (xx.xxx)	xx.xx (xx.xxx)	xx.xx (xx.xxx)	xx.xx (xx.xxx)
Median	XX.XX	XX.XX	XX.XX	XX.XX	XX.XX	XX.XX	XX.XX	XX.XX
Q1, Q3	xx.xx, xx.xx	xx.xx, xx.xx	xx.xx, xx.xx	xx.xx, xx.xx	xx.xx, xx.xx	xx.xx, xx.xx	xx.xx, xx.xx	xx.xx, xx.xx
Min, Max	xx.x, xx.x	xx.x, xx.x	xx.x, xx.x	xx.x, xx.x	xx.x, xx.x	xx.x, xx.x	xx.x, xx.x	xx.x, xx.x
etc.								

N = number of patients in analysis set; n = number of patients with data available.

SD = Standard deviation;Q1 = 25th percentile; Q3 = 75th percentile; Min = Minimum; Max = Maximum.

Notes: The Baseline value is defined as last scheduled or unscheduled non-missing value collected prior to the first dose of the first study drug administration. Reference: Listing 16.2.8.3.2

Programming notes (not part of the table):

- Table template TEG002B.
- Parameter is: Average QTcF interval (msec).

• Visits: Day 1 - Post-infusion, Day 3 - Post-infusion and Day 31.

• The displayed xxx do not reflect actual decimal precision. Please follow Section 2.11 for rounding rules.

xxx (xx.x)

xxx (xx.x)

xxx (xx.x)

xxx (xx.x)

Visit	Plitidepsin 2.5mg	Plitidepsin 1.5mg	Plitidepsin Total	Control Arm	
Parameter	(N=XXX)	(N=XXX)	(N=XXX)	(N=XXX)	
PCI Criterion	n (%)	n (%)	n (%)	n (%)	
< <day x="">> Patients at <<day x="">>, n1</day></day>	XXX	xxx	XXX	xxx	

xxx (xx.x)

xxx (xx.x)

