#### Table 14.3.6.2 Potentially Clinically Important (PCI) Electrocardiogram (ECG) Results (As Treated Population)

N = number of patients in analysis set; n = number of patients with data available; n1 = number of patients with data available at visit; % = percentages are calculated based on n1 as the denominator;

xxx (xx.x)

xxx (xx.x)

QTcF = QT correction as calculated by Fridericia's formula.

Change from baseline > 30 msec

Notes: The Baseline value is defined as last scheduled or unscheduled non-missing value collected prior to the first dose of the first study drug administration. Reference: Listing 16.2.8.3.2

Programming notes (not part of the table):

Average QTcF Interval >500 msec

etc.

- Table template TEG005A.
- Visits: Day 1 Post-infusion, Day 3 Post-infusion and Day 31.
- Follow first footnote for calculation of percentages.

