## Listing 16.2.8.3.2 12-Lead Electrocardiogram (ECG) - Average QTcF Interval (As Treated Population)

Treatment Group: << Plitidepsin 2.5mg/Plitidepsin 1.5mg/Control Arm>>

Site ID - Patient ID	Age/Sex/Race [a]	Visit	Date of Collection (Day) [b]	Average QTcF Interval (msec)*	> 500 msec [c]	Change from Baseline	Change from baseline > 30 msec [d]
XXXX-YYYYY	XX/X/X	XXXXXXXXX	DDMMMYYYY (XX)	XXXX	XXX	XXXX	XXX
123-456789	45/M/W	Screening Day 1 Day 3 Day 31	19JAN2018 (-1) 20JAN2018 (1) 22JAN2018 (3) 18FEB2018 (31)	419* 425 450 412		6 31 -7	Yes
etc.							

Notes: The Baseline value is defined as last scheduled or unscheduled non-missing value collected prior to the first dose of the first study drug administration.

\* Baseline value.

[a] For sex, F = Female; M = Male. For race, AI = American Indian or Alaska native; A = Asian; BA = Black or African American; PI = Native Hawaiian or Other Pacific Islander; W = White; O = Other; UN = Unknown.

[b] Relative to the start of study treatment.

[c] > 500 msec column is 'Yes' if the average QTcF interval value is greater than 500 msec.

[d] Change from baseline > 30 msec column is 'Yes' if change from baseline value is greater than 30 msec.

- Listing template LEG001B.
- Include all Visits available in data including any unscheduled Visit.
- Order by Site ID Patient ID and Visit.

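### Section 7.7.5 lets an untimed Day 1 ECG serve as baseline, although the QTcF shells make that ECG a post-infusion, post-baseline visit

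*SAP*

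**What the plan says.** Section 7.7.5 defines the ECG baseline in two steps. The general rule is: "The Baseline value will be defined as last scheduled or unscheduled non-missing value collected prior to the first dose of the first study drug administration". A default for the dosing day follows: "Assessments carried out on day of first study drug administration are considered to have taken place before the study drug administration", with the condition "if the corresponding times have not been recorded". The section then plans summaries of average QTcF and its change from baseline by visit. It also plans counts of patients with an average QTcF above 500 msec or a change from baseline above 30 msec.

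The schedule in Appendix 4 has ECGs at screening, Day 1, Day 3 and Day 31. Its note 4 reads: "QTcF prolongation to be assessed at screening and on Days 1, 3 (postinfusion), and 31 (±3 days".

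The table shells are more specific. For Table 14.3.6.1 the programming note is "Visits: Day 1 - Post-infusion, Day 3 - Post-infusion and Day 31". For Table 14.3.6.2 it is "Visits: Day 1 Post-infusion, Day 3 Post-infusion and Day 31". In the example rows of Listing 16.2.8.3.2 the screening value carries the baseline star, and a change from baseline is shown for Day 1.

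**The concern.** The default suits measurements that are scheduled before treatment on Day 1. Near-identical sentences appear in Section 7.7.3 for laboratory data and Section 7.7.4 for vital signs. There the schedule supports them: Appendix 4 places Day 1 chemistry before treatment starts and takes vital signs just before each plitidepsin infusion. Neither the schedule nor the shells show a separate pre-dose Day 1 ECG, so for ECGs the default presumes the opposite of what the shells expect.

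An untimed Day 1 ECG is therefore a baseline under Section 7.7.5 and a post-baseline value under the shells, and a programmer cannot satisfy both. If Section 7.7.5 is followed, an ECG taken after plitidepsin becomes the reference for every later visit of that patient. Two of the three QTcF summaries in the section, the mean change and the count above 30 msec, depend on that reference. The separately reported QTc substudy covers only about 50 patients (Section 2.2) and does not repair the main-study tables.

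**Working it through.** **Step 1. Is the scheduled Day 1 ECG before or after the infusion?**

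- Appendix 4, note 4: the bracketed word can be read as covering Day 3 only, so the note alone does not settle Day 1.
- Tables 14.3.6.1 and 14.3.6.2: both label the Day 1 visit as post-infusion and list it among the post-baseline visits. This settles it.
- Listing 16.2.8.3.2: screening is baseline and Day 1 has a change value, which agrees with the shells.

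**Step 2. Reproduce the listing's example.** Inputs are the mock QTcF values: screening 419, Day 1 425, Day 3 450, Day 31 412 msec. Change = visit value − baseline value.

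| Visit | Baseline = screening (419) | Baseline = untimed Day 1 (425) |
|---|---|---|
| Day 1 | 425 − 419 = +6 | 425 − 425 = 0, or no row |
| Day 3 | 450 − 419 = +31, flagged | 450 − 425 = +25, not flagged |
| Day 31 | 412 − 419 = −7 | 412 − 425 = −13 |

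The middle column matches the listing (6, 31, −7, with the Day 3 flag set). The right-hand column is what Section 7.7.5 gives if the Day 1 time is missing. Each later change shifts down by Day 1 minus screening, here 6 msec. These are invented example data, so they show the mechanism and not its frequency or true size.

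**Step 3. How the effect scales.** The documents give neither a QTcF effect for plitidepsin nor the untimed share. The following are assumptions: an equal mean drug effect d on Days 1 and 3, a normally distributed change with SD s whichever ECG is the baseline, and a share f of plitidepsin patients with an untimed Day 1 ECG.

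- Mean Day 3 change = d × (1 − f).
- Correct proportion above 30 msec: P = 1 − Φ((30 − d)/s).
- For an untimed patient the drug effect cancels: P₀ = 1 − Φ(30/s).
- Observed proportion = (1 − f) × P + f × P₀.

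With d = 10 and s = 15, P = 1 − Φ(1.33) = 0.0912 and P₀ = 1 − Φ(2) = 0.0228.

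| d | s | f | Mean Day 3 change (msec) | Correct P(>30) | Observed P(>30) |
|---|---|---|---|---|---|
| 5 | 10 | 0.05 | 4.75 | 0.0062 | 0.0060 |
| 10 | 15 | 0.05 | 9.5 | 0.0912 | 0.0878 |
| 10 | 15 | 0.20 | 8.0 | 0.0912 | 0.0775 |
| 10 | 15 | 1.00 | 0 | 0.0912 | 0.0228 |
| 20 | 15 | 0.20 | 16.0 | 0.2525 | 0.2065 |

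The mean change shrinks in direct proportion to the untimed share. At a few per cent the effect is small. It becomes material only if untimed Day 1 ECGs are common.

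**The case against.** The strongest reply is that this is a narrow fallback. It acts only when a clock time is missing. Listing 16.2.8.3.1 has a date and time field for every ECG replicate, and nothing in the documents suggests that Day 1 times are absent. The shells and the mock listing also show what was intended, so the remaining task is to align the text of Section 7.7.5 with them. This stands as a limit on the size of the problem. It does not remove the conflict, because the written rule still decides what happens to an untimed ECG.

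A reader might infer that control is untouched because it has no infusion. That is not right. Control patients receive intravenous dexamethasone on Days 1 to 3 (Section 2.2) and may receive intravenous remdesivir (Appendix 4), and baseline is anchored to the first dose of any study drug. The rule therefore applies in all arms. Only a plitidepsin-specific effect on QTcF would make its consequence differ by arm.

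A reader might also infer that every affected change is reduced. For one patient the shift is Day 1 minus screening, which is drug effect plus ordinary variation and can take either sign. Attenuation holds on average, and only if plitidepsin prolongs QTcF.

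Finally, the default has a proper use. Screening is labelled Day 0-1 in Appendix 4, so a screening ECG may fall on the dosing day. An untimed one should stay eligible as baseline. Deleting the default by calendar day could leave such a patient without a baseline.

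**Conclusion.** The conflict is real and should be corrected. As written, Section 7.7.5 assigns an untimed Day 1 ECG to baseline, while both QTcF table shells treat that ECG as post-infusion and post-baseline. For affected patients the Day 1 change is lost, and any Day 1 drug effect is on average removed from the Day 3 and Day 31 changes. If plitidepsin prolongs QTcF, the mean change and the count above 30 msec are biased toward masking it in the two plitidepsin arms.

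The size cannot be stated from the documents. It scales with the share of patients whose Day 1 ECG time is missing, which is not given and may be zero.

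A reader might infer that QTcF prolongation is hidden in this trial. The documents do not support that. They report no missing times and state no QTcF effect. The criterion above 500 msec on Days 3 and 31 does not use baseline, and the raw values stay in Listings 16.2.8.3.1 and 16.2.8.3.2.

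**What to change.** In Section 7.7.5, tie the rule to the visit label and not to the calendar day. State that an ECG recorded under the Day 1 post-infusion visit is never eligible as baseline, whether or not its time is recorded, in all arms. Baseline is then the last ECG recorded under the screening visit, including an untimed one on the dosing day, or a later ECG with a recorded pre-dose time. Reword note 4 of Appendix 4 so that it says plainly whether Day 1 is post-infusion.

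The cost is one sentence and one programming condition, plus a slightly older baseline for the affected patients. The SAP addendum (Section 1) gives the database lock as 26 April 2023, so untimed Day 1 ECGs can be counted directly. If there are none, no result changes. If there are some, Tables 14.3.6.1 and 14.3.6.2 and Listing 16.2.8.3.2 need to be checked and, where Day 1 was used as baseline, rerun.

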### 7.7.3 Laboratory Evaluations

Data for the haematology, serum chemistry, and coagulation analytes received from central laboratory will be listed and summarized by treatment group and overall plitidepsin, and visit. Haematology and serum chemistry analytes from local laboratories recorded at Screening in the eCRF will be listed only. If data for any additional analytes are also received then these will be listed only.

Immunology and Serological SARS CoV 2 data are summarised within the other secondary efficacy endpoints.

Haematology	Serum Chemistry	
Red Blood Cell Count	Alanine aminotransferase (ALT)	
Haemoglobin	Aspartate aminotransferase (AST)	
Haematocrit	Alkaline phosphatase	
White Blood Cell Count	Gamma-Glutamyltransferase (GGT)	
Neutrophils	LDH	
Eosinophils	Total Bilirubin	
Basophils	Direct Bilirubin	
Lymphocytes	Glucose (fasting)	
Monocytes	Sodium	
Platelet Count	Potassium	
Transunalagy	Calcium (adjusted)	
Immunology	Magnesium	
CRP	Blood Urea Nitrogen	
Ferritin	Creatinine	
IL-1β	Calculated Creatinine Clearance (Cockcroft-Gault equation)	
IL-6	Creatine Phosphokinase (CPK)	
IL-10	Albumin	
TNFa	Amylase	
	Lipase	
Other Samples	Procalcitonin	
Pregnancy tests (females	Troponin T	
only)	N-terminal pro-B-type natriuretic peptide (NT-pro-BNP)	
Coagulation	Serological SARS CoV 2 testing	
D-dimer	IgG	

All central Laboratory data will be reported in International System of Units. Local Laboratory data will be listed in the Units that they were collected in the eCRF. Outof-reference-range values will be flagged as high (H) or low (L) in the listings. For analysis purposes, values preceded by a "<" or a ">" sign (ie, those below or above the limits of quantification) will be considered equal to the lower or upper limit of quantification, respectively.

Central laboratory data will be summarized by visit using standard descriptive statistics by treatment group and overall plitidepsin for the As Treated population. Changes from Baseline will also be summarized. For post-Baseline, only data from scheduled visits will be included in the summary tables.

If more than 10% of the patients preform an unscheduled central laboratory assessment at the same relative day to the start date of study treatment then the central laboratory data will be also summarised at the specific relative day. In case of several unscheduled laboratory assessments at the same day we will use the worst result.

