For each laboratory analyte, the Baseline value will be defined as last scheduled or unscheduled non-missing value from central Laboratory collected prior to the first dose of the first study drug administration. Central Laboratory assessments carried out on the day of first study drug administration are considered to have taken place before the study drug administration, if the corresponding times have not been recorded.

For haematology and serum chemistry analytes, laboratory abnormalities from central Laboratory analytes will be graded according to NCI-CTCAE version 5.0. Shift tables presenting the number and percentage of patients cross-tabulating NCI CTC grade at baseline to the worst grade after baseline through the study (including results from unscheduled visits) will be provided by treatment group for the As Treated population. For analytes that have NCI-CTCAE gradings for both low and high values, low and high will be summarized separately. In the shifts of low values, any high values will be classified as normal and the worst low grade will be summarized. And in the shifts of high values, any low values will be classified as normal and the worst high grade will be summarized.

Haematology analyte	Low NCI CTC grade	High NCI CTC grade
Red Blood Cell Count	-	-
Haemoglobin	Х	Х
Haematocrit	-	-
White Blood Cell Count	Х	Х
Neutrophils (absolute)	Х	-
Eosinophils (absolute)	-	Х
Basophils (absolute)	-	-
Lymphocytes (absolute)	Х	Х
Monocytes (absolute)	-	-
Platelet count	Х	-

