### 7.7.4 Vital Signs

The following vital signs and  $SpO_2$  at room air (%) by pulse oximetry will be listed and summarized by treatment group and visit.

- systolic and diastolic blood pressure (mmHg);
- pulse rate (beats/min);
- temperature (°C);
- respiration rate (breaths/min).

Vital signs and SpO2 at room air (%) data and their changes from baseline will be summarized by visit using standard descriptive statistics by treatment group and overall plitidepsin for the As Treated population. The baseline value will be defined as last scheduled or unscheduled non-missing value collected prior to the first dose of the first study drug administration. Assessments carried out on day of first study drug administration are considered to have taken place before the study drug administration, if the corresponding times have not been recorded. For postbaseline, only data from scheduled visits will be included in the summary tables

If more than 10% of the patients preform an unscheduled vital signs assessment at the same relative day to the start date of study treatment then the vital signs and  $SpO_2$  at room air data will be also summarised at the specific relative day. In case of several unscheduled vital signs and  $SpO_2$  at room air assessments at the same day we will use the worst result.

For the above summaries, the vital signs and SpO2 at room air (%) assessed just before the start and immediately at the end of the plitidepsin infusion (for patients randomised to plitidepsin arms) will not be taken into account. These assessments will be summarized separately, the vital signs and SpO2 at room air (%) assessed just before the start and immediately at the end of the plitidepsin infusion; and the change from the start to the end of the plitidepsin infusion (end of the plitidepsin infusion value – start of the plitidepsin infusion value) will be summarized by visit for the plitidepsin arms and overall plitidepsin using standard descriptive statistics for the As Treated population.

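### Table 14.3.6.2 counts QTcF above 500 msec and rises above 30 msec at three scheduled visits only, so no table gives the number of patients who ever crossed either limit

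*SAP*

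**What the plan says.** Section 7.7.5 defines two potentially clinically important results. One is "Average QTcF interval value > 500 msec"; the other is a rise from baseline in QTcF of more than 30 msec. Both are to be tabulated by treatment group, overall plitidepsin and visit in the As Treated population. For which ECGs count, the section says: "For post-baseline, only data from scheduled visits will be included in the summary tables".

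The shell for Table 14.3.6.2 follows this. Its programming note reads "Visits: Day 1 Post-infusion, Day 3 Post-infusion and Day 31", and its footnote sets the denominator: "n1 = number of patients with data available at visit; % = percentages are calculated based on n1 as the denominator". There is no worst-value row, no any-time row and no place for an unscheduled ECG. Table 14.3.6.1, the only other QTcF table, gives descriptive statistics at the same three visits.

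Listing 16.2.8.3.2 carries a flag for each of the two limits on every record, and its note says "Include all Visits available in data including any unscheduled Visit".

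**The concern.** For a threshold result, a safety reader wants the number of patients per arm who crossed at any time on study. The by-visit table does not give it, for two separate reasons:

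- An unscheduled ECG is often the one taken because something looked wrong, and it is excluded from every row.
- Even among scheduled ECGs, one patient may appear in one, two or three rows, each with its own denominator, so the rows cannot be combined into a patient count.

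The SAP gives this result weight. ECG variation is a named safety objective (Section 2.1.3.2) and endpoint (Section 3.4). The ECG note to the schedule in Appendix 4 says any QTcF value above 500 msec is to be flagged as raising the likelihood that treatment is proarrhythmic. The table that summarises the limit nevertheless looks at three fixed time points only. What is at stake is the completeness of a descriptive safety count, not any inference.

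**Working it through.** The SAP states no figure for this point, so there is none to reproduce. The check sets the rules side by side and then asks what the table can and cannot tell a reader.

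**Does the restriction reach the threshold counts?** In Section 7.7.5 the scheduled-only sentence comes just before the paragraph on the two limits, so it could be read as covering only the descriptive statistics. The visit list in Table 14.3.6.2 settles this: the threshold counts use the same three scheduled visits.

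**How does the SAP treat unscheduled values elsewhere?**

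| Data | By-visit default | Route for unscheduled values into a summary |
|---|---|---|
| Laboratory (7.7.3) | Scheduled visits | Extra summary at a relative day: "If more than 10% of the patients preform an unscheduled central laboratory assessment at the same relative day". Shift tables use "the worst grade after baseline through the study (including results from unscheduled visits" |
| Vital signs (7.7.4) | Scheduled visits | Extra summary at a relative day: "If more than 10% of the patients preform an unscheduled vital signs assessment at the same relative day" |
| ECG (7.7.5) | Scheduled visits | None; listed only |

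The close parallel is the laboratory shift table. For graded abnormalities the SAP itself takes the worst post-baseline result from all visits.

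**Do the adverse event tables supply the count?** Sections 7.7.6 and 7.7.7 say that clinically significant physical-examination and chest-imaging findings are recorded as medical history, sign and symptom, or adverse event, and summarised there. Section 7.7.5 has no such statement for ECG. A crossing may be reported as an adverse event, but the SAP does not say that it must be.

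**What can be recovered from the three rows?** Let a, b and c be the numbers crossing at Day 1, Day 3 and Day 31 in one arm. The number who crossed at one or more scheduled visits lies between

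- max(a, b, c), if the patients overlap as much as possible, and
- a + b + c, if no patient appears twice.

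| Counts (a, b, c) | Fewest patients | Most patients |
|---|---|---|
| 1, 1, 1 | 1 | 3 |
| 2, 2, 2 | 2 | 6 |
| 3, 2, 1 | 3 | 6 |

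The ratio of most to fewest is at most 3, the number of scheduled rows, and reaches 3 only when the three counts are equal. A patient who crosses only on an unscheduled ECG adds 0 to a, b and c and comes on top of these totals. No arm size or event rate is assumed.

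**The case against.** The text, the shell and the ECG schedule agree with one another: Section 7.7.5 promises counts by visit and the table delivers them at the scheduled ECG days. Nothing is misstated. Nothing is lost either, because Listing 16.2.8.3.2 is arranged by treatment group and patient, includes unscheduled visits and flags both limits, so the ever-crossed count can be obtained exactly by counting patients with a flag. The trial also has other cardiac reporting: a QTc substudy of about 50 patients under its own SAP, and cardiac events of special interest counted once per patient. Finally, restricting a between-arm table to scheduled visits is defensible in an open-label trial, where unscheduled ECGs may be taken more often in one arm.

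Much of this stands. There is no contradiction in the SAP, and the harm is that a count has to be made by hand. The 10% rule for laboratory data and vital signs is weak support for the concern: it adds a summary at a single day and would not pick up isolated crossings. The three-fold range is arithmetic that holds for any three-visit table and is not an estimate of an effect. The extreme also needs as many crossings at Day 31, four weeks after a three-day course, as on Days 1 and 3.

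The case does not remove the gap. A listing is not a per-arm summary, the special-interest tables count reported events and not threshold crossings, and the substudy covers only a subset. The ascertainment point is a reason to keep the by-visit rows as the main comparison. It is not a reason to leave out the patient count.

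**Conclusion.** The concern holds. If Section 7.7.5 and the shell are followed, the only table that counts QTcF limit crossings omits every crossing seen only on an unscheduled ECG, and it does not give the number of patients who ever crossed. For scheduled visits alone, the by-visit counts leave that number uncertain by a factor of up to three. The SAP gives neither a crossing rate nor a number of unscheduled ECGs, so the actual undercount, and which arm it would favour, cannot be stated. No hypothesis test, estimate or error rate is touched. This is a worthwhile improvement to a descriptive safety table and should be made.

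**What to change.** In Section 7.7.5 and Table 14.3.6.2, keep the three by-visit blocks and add one row per criterion for any post-baseline ECG, scheduled or unscheduled:

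- Average QTcF above 500 msec: denominator, patients with at least one post-baseline ECG.
- Rise from baseline above 30 msec: the same denominator, restricted to patients who also have a baseline value.

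Next to these rows, show the number of post-baseline ECGs per patient by arm.

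The cost is two rows and one count line in a single table, from data already in Listing 16.2.8.3.2. Database lock is no obstacle, since Section 1 of the SAP addendum allows further tables; its present output list has none for ECG. The drawback is ascertainment: in this open-label trial an arm with more unscheduled ECGs has more chances to cross. The by-visit rows should therefore remain the main between-arm display, and the new rows should be read together with the ECG counts.
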